#### Part C

Part C will assess the interaction of LY3323795 with itraconazole, a CYP3A inhibitor. The dose of LY3323795 administered in this part of the study will be the same as, or lower than, a dose that was safely administered in Part A. The dose will be no greater than one-tenth of the MTD administered in Part A. The planned itraconazole dose (200 mg) has been safely administered in previous drug interaction studies of this design.

**Table SCAA.2. Margin of Safety for Oral Administration of LY3323795 Based on Administered Dose and Predicted Exposure**

	Dose (mg/kg)	Dose (mg/m  )	Dose Multiple a	AUC (µg·hour/mL) or C max (ng/mL)	Exposure Multiple a
Human b (0.3 mg)		0.2	-	0.0245 or 0.627	-
Rat NOAEL c	150	900	4500	M=34.5 or 2140 F=91.5 or 4950	M=1408 F=3735
Dog NOAEL d	120	2400	12,000	51.8 or 3095	2114
QTc LOEL (5 mg/kg) Day 1 TK	NA	NA	NA	C max =1018 C max multiple=1623	-
Human b (100 mg)		52.9	-	8.18 or 210	-
Rat NOAEL c	150	900	17	M=34.5 or 2140 F=91.5 or 4950	M=4 F=11
Dog NOAEL d	120	2400	45	51.8 or 3095	6
QTc LOEL (5 mg/kg) Day 1 TK	NA	NA	NA	C max =1018 C max multiple=5	

Abbreviations: AUC = area under the plasma concentration-versus-time curve; Cmax = maximum drug concentration; F = female; LOEL = lowest-observed-effect-level; M = male; NA = not applicable; NOAEL = no-observed-adverse-effect level; QTc = QT corrected for heart rate; TK = toxicokinetics.

- a Dose multiple is the dose in animals/dose in humans based on mg/m^2. Exposure multiple is the calculated AUC in animals/projected AUC in humans (Projected human exposures located in Table 5.7 of the IB).
- b Day 28 AUC from the repeat-dose toxicity study in either rats or dogs (as indicated), unless otherwise specified.
- c NOAEL determined in a 1-month repeat-dose toxicity study in rats (Report 8339313).
- d NOAEL determined in a 1-month repeat-dose toxicity study in dogs (Report 8339298).

## 6. Study Population

Eligibility of subjects for study enrollment will be based on the results of a screening medical history, physical examination, vital signs, clinical laboratory tests, ophthalmic examination, and ECGs. The nature of any conditions present at the time of the physical examination and any preexisting conditions will be documented.

A generic screening informed consent may be used for screening procedures. Screening may occur up to 28 days prior to enrollment. Subjects who are not enrolled within 28 days of screening may be subjected to an additional medical assessment and/or clinical measurements to confirm their eligibility.

Prospective approval of protocol deviations to recruitment and enrollment criteria, also known as protocol waivers or exemptions, is not permitted.

### 6.1. Inclusion Criteria

Subjects are eligible for inclusion in the study only if they meet all of the following criteria at screening and/or enrollment:

- [1] are overtly healthy males or females, as determined by medical history and physical examination.
  - [1a] male subjects must agree to use an effective method of birth control during the study and for 3 months following the last dose of the investigational product. At least 1 effective method of contraception will be used (eg, condoms with spermicide, male sterilization, oral contraceptive pill, intrauterine device, etc.). The subject may choose to use a barrier method of contraception. Barrier protection methods without concomitant use of a spermicide are not an effective or acceptable method. Thus, each barrier method must include use of a spermicide (ie, condom with spermicide, diaphragm with spermicide, female condom with spermicide). However, the use of male and female condoms as a double barrier method is not considered acceptable due to the high failure rate when these barrier methods are combined.
  - [1b] female subjects are of nonchildbearing potential if they have undergone surgical sterilization (hysterectomy or bilateral oophorectomy or tubal ligation) or are postmenopausal (defined as women aged at least 45 years with an intact uterus, who have not taken hormones or oral contraceptives for >1 year), and have either:
    - [i] spontaneous amenorrhea for 6 to 12 months, not induced by a medical condition such as anorexia nervosa and not taking medications that induced the amenorrhea (eg, oral contraceptives, hormones, gonadotropin-releasing hormone, anti-estrogens, selective estrogen receptor modulators, or chemotherapy);
    - [ii] a follicle-stimulating hormone level >40 mIU/mL

- [2] are aged at least 20 years at the time of screening
- [3] have a body mass index (BMI) between 18.0 kg/m^2 and 32.0 kg/m^2, inclusive
- [4] have clinical laboratory test results within normal reference range for the population or investigative site, or results with acceptable deviations (with the exception of liver tests, which must be below the upper limit of normal [ULN]) that are judged to be not clinically significant by the investigator
- [5] have venous access sufficient to allow for blood sampling as per the protocol
- [6] are reliable and willing to make themselves available for the duration of the study and are willing to follow study procedures and research unit policies
- [7] have given written informed consent approved by Lilly and the ethical review board (ERB) governing the site

## 6.2. Exclusion Criteria

Subjects will be excluded from study enrollment if they meet any of the following criteria at screening and/or enrollment:

- [8] are investigative site personnel directly affiliated with this study and their immediate families. Immediate family is defined as a spouse, or biological or legal guardian, child, or sibling
- [9] are Lilly employees or employees of Parexel
- [10] are currently enrolled in a clinical trial involving an investigational product or any other type of medical research judged not to be scientifically or medically compatible with this study
- [11] have participated, within the last 30 days, in a clinical trial involving an investigational product. If the previous investigational product has a long half-life, 3 months or 5 half-lives (whichever is longer) should have passed
- [12] have previously completed or withdrawn from this study or any other study investigating LY3323795, and have previously received the investigational product
- [13] have known allergies to LY3323795, related compounds, or any components of the formulation, itraconazole (if the subject is assigned to Part C), or history of significant atopy
- [14] have a QTc (using Bazett's formula) interval value of >450 msec (males) or >470 msec (females) or any abnormality in the 12-lead ECG that, in the opinion of the investigator, increases the risks associated with participating in the study
- [15] have clinically significant abnormal blood pressure as determined by the investigator

- [16] have a history or presence of cardiovascular, respiratory, hepatic, renal, gastrointestinal, endocrine, hematological, or neurological disorders capable of significantly altering the absorption, metabolism, or elimination of drugs; of constituting a risk when taking the investigational product; or of interfering with the interpretation of data
- [17] have known or ongoing psychiatric disorders, or active neuropsychiatric disease deemed clinically significant in the opinion of the investigator
- [18] regularly use known drugs of abuse and/or show positive findings on urinary drug screening
- [19] show evidence of human immunodeficiency virus (HIV) infection and/or positive human HIV antibodies
- [20] show evidence of hepatitis C and/or positive hepatitis C antibody
- [21] show evidence of hepatitis B and/or positive hepatitis B surface antigen
- [22] are women who are lactating
- [23] have used or intend to use over-the-counter or prescription medication (including herbal medications) within 14 days prior to dosing or during the study, with the exception of vitamins and mineral supplements (not providing >100% of the recommended dietary allowance [RDA]), occasional paracetamol/acetaminophen up to 2-g dose in a 24-hour period, and/or hormone replacement therapy or thyroid replacement therapy. If this situation arises, inclusion of an otherwise suitable subject may be at the discretion of the sponsor
- [24] have donated blood >500 mL within the last month
- [25] have an average weekly alcohol intake that exceeds 3 units per day or 21 units per week (males up to age 65 years) and 14 units per week (females, and males older than 65 years), or are unwilling to stop alcohol consumption 48 hours prior to dosing until the completion of each study period (1 unit = 12 oz or 360 mL of beer; 5 oz or 150 mL of wine; 1.5 oz or 45 mL of distilled spirits)
- [26] have an increased risk of seizures as evidenced by a history of head trauma with loss of consciousness within the last 5 years or  $\geq 1$  seizure (except childhood febrile seizure); have prior electroencephalogram with epileptiform activity; or surgery to the cerebral cortex
- [27] have a history of clinically significant stroke that is deemed to be a risk to subject participation in the study, in the opinion of the investigator
- [28] have a history of, or current, significant ophthalmic disease in the opinion of the investigator

- [29] are unwilling or unable to refrain from eating any food or drinking any beverage containing grapefruit or grapefruit juice (or other restricted foods as listed in Section 6.3.1) for at least 2 weeks prior to first dose until completion of the study
- [30] consume more than 10 cigarettes per day or unable/unwilling to abide by CRU smoking restrictions before and during admissions
- [31] in the opinion of the investigator and/or sponsor, are unsuitable for inclusion in the study

**In addition, for Part B only:**

- [32] show clinically significant abnormalities in lumbar spine previously known or determined by screening lumbar x-ray (if conducted) that are considered incompatible with LP by the investigator and/or the person conducting the LP (if not the investigator)
- [33] have a history of clinically significant back pain, back pathology, and/or back injury (eg, degenerative disease, spinal deformity, or spinal surgery) that may predispose to complications or technical difficulty with LP
- [34] have evidence or history of significant active bleeding or coagulation disorder or have taken nonsteroidal anti-inflammatory drugs or other drugs that affect coagulation or platelet function within 14 days prior to lumbar catheter insertion
- [35] have an allergy to lidocaine (Xylocaine®) or its derivatives
- [36] have medical or surgical conditions in which LP/lumbar catheterization is contraindicated

### **6.3. Lifestyle and/or Dietary Requirements**

Throughout the study, subjects may undergo medical assessments and review of compliance with requirements before continuing in the study.

#### **6.3.1. Meals and Dietary Restrictions**

**Fasting** – For all parts of the study, subjects will be required to fast overnight (at least 8 hours) prior to each dosing day and for at least 4 hours after LY3323795 or placebo dosing, with the exception of water that will be freely available before and after dosing. However, no water is allowed 1 hour prior to ECG measurement.

For Part C, there will be no fasting required before or after dosing itraconazole alone. However, for coadministration of itraconazole with LY3323795, subjects will be required to fast overnight (at least 8 hours) prior to and for at least 4 hours after LY3323795 dosing.

**Grapefruit** – Subjects should refrain from eating any food or drinking any beverage containing grapefruit, pomelo, star fruit, Seville oranges, or juice from any of these fruits, from 2 weeks prior to dosing until completion of the study.

**Hydration** – Subjects should be adequately hydrated throughout the study. Therefore, subjects should be encouraged to drink several glasses of water each day.

### **6.3.2. Caffeine, Alcohol, and Tobacco**

**Caffeine** – Consumption of caffeine- and xanthine-containing products is allowed, provided that the subject's consumption has been consistent for the last 30 days, and will remain consistent throughout the duration of the study.

**Alcohol** – Subjects will not be permitted to consume alcohol from 48 hours prior to CRU admissions until after the last PK sample is collected for each study period. During outpatient periods, male subjects should be advised to limit alcohol consumption to no more than 21 units per week and female subjects to no more than 14 units per week, and all subjects should be advised to limit alcohol consumption to no more than 3 units in a day.

**Tobacco** – Subjects will not be permitted to smoke from 24 hours before visiting the CRU until discharge from the CRU.

### **6.3.3. Activity/Other Requirements**

Subjects should avoid strenuous physical activity 48 hours prior to CRU visit and until final discharge from the study.

Subjects should avoid exposure to the sun, and not use sun lamps or tanning beds throughout the duration of the study. High-factor sunscreen should be used if prolonged sun exposure is unavoidable.

Blood or plasma donations are not permitted while participating in the study.

## **6.4. Screen Failures**

Individuals who do not meet the criteria for participation in this study (screen failure) will not be allowed to rescreen.

## 7. Treatment

### 7.1. Treatment Administered

This study involves a comparison of LY3323795 and placebo over a planned dose range of 0.3 mg to 100 mg in Parts A and B, and administration of LY3323795 alone and with itraconazole in Part C. [Table SCAA.3](#) shows the treatment regimens.

After an overnight fast (see Section 6.3.1), capsules of LY3323795 or placebo will be administered orally with approximately 240 mL of room-temperature water in the morning of each dosing day.

For Part A, subjects should remain upright (standing or sitting) for at least 4 hours after dosing, with the exception of any requirements for protocol procedures (eg, supine for ECGs). For Part B, subjects will be encouraged to remain supine for the entire lumbar catheterization period.

In Part C, itraconazole will be administered as an oral solution with extra water if subjects prefer. No fast is required before or after dosing with itraconazole alone.

To ensure blinding is maintained in each cohort in Parts A and B, subjects assigned to LY3323795 and those assigned to placebo will receive the same number of capsules. In Part A, the number of capsules between periods may vary based on dose-escalation decisions, but within a period, all subjects will receive the same number of capsules.

**Table SCAA.3. Treatments Administered**

Treatment Name	LY3323795	Placebo	Itraconazole
Dosage Formulation	0.3-, 1-, and 10-mg capsules	Capsules to match	10 mg/mL solution
Planned Dosage Levels	0.3, 1, 3, 10, 30, and 100 mg	-	200 mg
Route of Administration	Oral	Oral	Oral

The investigator's designee is responsible for:

- explaining the correct use of the investigational product(s) to the site personnel,
- verifying that instructions are followed properly,
- maintaining accurate records of investigational product dispensing and collection,
- returning all unused medications to Lilly or its designee at the end of the study.

In some cases, sites may destroy the material if, during the investigative site selection, the evaluator has verified and documented that the site has appropriate facilities and written procedures to dispose of clinical trial materials. Subjects will be instructed to contact the investigator as soon as possible if he or she has a complaint or problem with the investigational product so that the situation can be assessed. All clinical trial materials provided to the investigator will be stored in a secure place and allocated and dispensed by appropriately trained persons. The allocation and dispensing of the investigational products will be fully documented and verified by a second person. Detailed records of the amounts of the investigational product received, dispensed, and remaining at the end of the study will be maintained.

### **7.1.1. Packaging and Labeling**

Clinical trial materials will be labeled according to the country's regulatory requirements. Each capsule of LY3323795 will be size 2, blue in color and will contain 0.3 mg, 1 mg, or 10 mg of active ingredient. Placebo capsules will match LY3323795 capsules in appearance. LY3323795 and matching placebo capsules will be supplied to the investigator by Lilly for dispensing by unblinded pharmacy staff.

CCI

Clinical trial materials will be manufactured in accordance with good manufacturing practice. All drug supplies will be labeled according to applicable local regulatory requirements.

## **7.2. Method of Treatment Assignment**

Randomization tables for allocation of LY3323795 and placebo will be prepared by the Lilly statistician.

### **7.2.1. Selection and Timing of Doses**

Doses of LY3323795 will be administered at approximately the same time on each day. The actual time of all dose administrations will be recorded in the subject's case report form (CRF). For LY3323795 or placebo dosing, the dosing time is defined as the time when the first capsule is swallowed.

## **7.3. Blinding**

This study will be subject- and investigator-blinded except in Part C (itraconazole interaction), which will be open-label. To preserve the blinding of the study, a minimum number of Lilly personnel will see the randomization table and treatment assignments before the study is complete. The randomization tables will be provided to the study site pharmacists or pharmacy staff involved in dose preparation.

As dosing occurs in the study, the pharmacy staff will document dosing at the site using an accountability log. Individuals involved with study drug preparation will not be involved in any clinical aspects of the study, including study drug administration and AE assessments. The sponsor team will not be blinded and may see the randomization tables and/or treatment table before the end of the study but this will be kept to a minimum. While the study blind is in effect,

individuals with access to the randomization tables and/or treatment table will not share the identifying information with investigative site staff involved with direct subject care or safety assessments. An exception is if sharing such information is required for emergency unblinding.

AEs and clinical safety abnormalities will be interpreted with the subject- and investigator-blind intact, on the assumption that active study drug was administered. If the AE is a clinically significant event (CSE), the investigator should judge whether the CSE is related to study drug administration while remaining blinded. A CSE will be defined as a moderate-to-severe AE, abnormal clinical sign, or clinical laboratory finding that may pose a risk to the well-being of the subject.

Emergency codes will be available to the investigator. A code, which reveals the treatment group for a specific study subject, may be opened during the study only if the subject's well-being requires knowledge of his/her treatment assignment.

In case of an emergency, the investigator has the sole responsibility for determining if unblinding of a subject's treatment assignment is warranted for medical management of the event. Subject's safety must always be the first consideration in making such a determination. If the investigator decides that unblinding is warranted, the investigator should make every effort to contact the Lilly clinical pharmacologist or clinical research physician (CRP) prior to unblinding a study subject's treatment assignment unless this could delay emergency treatment of the subject. If a study subject's treatment assignment is unblinded, Lilly must be notified immediately.

If a subject's study treatment assignment is unblinded, the subject must be discontinued from the study, unless the investigator obtains specific approval from a Lilly clinical pharmacologist or CRP for the study participant to continue in the study.

Upon completion of the study, all emergency codes must be returned to Lilly or its designee.

A detailed blinding/unblinding plan will be issued to the study site.

## **7.4. Dose Modification**

### **7.4.1. Dose Decision/Escalation**

By nature of being a dose-escalation study, data will be evaluated on an ongoing basis until the MTD is determined or the highest planned dose (that is lower than the MTD) has been administered. The highest dose level that is tolerated will be designated as the MTD.

Safety data will be the primary criteria for the dose escalation. As described in Sections 5.1.1.1 and 5.1.2.1, certain dose-escalation decisions will also be based on PK ( $C_{max}$ , AUC, and clearance) data where available. No dose escalation can occur without prior discussion and agreement between the investigator and the Lilly clinical pharmacologist/CRP/study team.

Safety data, in particular AEs, SAEs, and adverse laboratory abnormalities, will be independently assessed by the investigator, and will be considered related to the investigational product unless there is clear evidence that the event is not related. See Section 10.3.1 for details.

After review of these data, an agreement on the appropriate dose escalation will be made by the investigator and sponsor for the next cohort. The magnitude of the dose escalation may be reduced following data review, but subsequent escalations cannot be increased by more than 3.3 times the original dose (a half-log increment).

If any of the following scenarios occur, dosing at the current level and further dose escalation will be discontinued:

- 1) a single subject experiences an SAE that is considered related to LY3323795 administration;
- 2)  $\geq 2$  subjects at the same dose level experience moderate or severe AEs that impair normal activities, and are considered related to LY3323795, but do not meet the CSE criteria;
- 3)  $\geq 2$  subjects at the same dose level experience similar CSEs considered related to LY3323795;
- 4)  $\geq 2$  subjects at the same dose level have an ophthalmic finding considered related to LY3323795;
- 5)  $\geq 2$  subjects, at any dose of LY3323795, have a QTc reading (mean of 3) that is  $>500$  msec or an increase of  $>60$  msec above the mean QTc control value for at least 2 consecutive time points. The mean QTc control value (mean of 3) is defined as the average of the Day 1, predose ECGs of the corresponding period.

Dosing may continue, if deemed appropriate by the investigator and sponsor, at doses lower than those that resulted in the dose escalation being stopped.

In the event of an SAE that is related to study drug, precautionary inpatient observation will be implemented, and dosing may be suspended. Dosing of a subject may resume only after the investigator and sponsor agree that it is appropriate to continue.

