**Figure SCAA.1. Illustration of study design for Protocol I9F-MC-SCAA.**

### **5.1.1. Part A: Dose-Escalation Study**

Part A is a dose-escalation study that will be conducted in 2 alternating cohorts (Cohorts 1 and 2), each consisting of approximately 9 subjects (6:3 subjects, LY3323795:placebo at each dose level) who will participate in 3 study periods (total of 6 dose levels in the 2 cohorts). The number of subjects intended to be enrolled is detailed in Section 5.2. The first 4 dose levels of LY3323795 are anticipated to be 0.3 mg, 1 mg, 3 mg, and 10 mg. Doses 5 and 6 are anticipated to be 30 and 100 mg, but will be confirmed following PK data reviews. See Section 5.1.1.1 for details of dose-escalation decisions.

Sentinel dosing will be used in this study. For all dose levels, LY3323795 and placebo will be administered first to a sentinel group of 2 subjects (1:1, LY3323795:placebo). These subjects will be followed for 24 hours postdose; if the dose is well tolerated, dosing of the remaining 7 subjects in the cohort may begin.

The proposed dose levels may be adjusted based on emerging safety and PK data (see Section 7.4.1).

Subjects will be admitted to the CRU on Day -1 (see Part A Schedule of Activities, Section 2) and will remain as inpatients for at least 48 hours after dosing on Day 1, after which they may be discharged at the discretion of the investigator. Subjects will then return for outpatient visits for up to 144 hours postdose (Day 7). The washout time between doses for a given subject will be at least 14 days.

PK and PD (plasma A $\beta$ ) data, as well as safety assessments, including clinical laboratory tests, ECGs, AEs, vital signs, ophthalmic examinations, and neurological surveys, will be collected at various time points pre- and postdosing with LY3323795/placebo, as described in Part A Schedule of Activities (Section 2). However, exact time points for PK/PD and safety assessments may be modified based on interim PK/PD results (see Section 5.1.1.1).

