#### **5.1.1.1. Dose Escalation and Interim Access to Data in Part A**

The decision to dose escalate will be based on safety reviews conducted after each dose (and PK reviews from Dose 4 [planned to be 10 mg] onwards). Dose escalation will not occur until after a review of at least 3 days' safety data from the preceding dose level has been carried out, and the dose shown to be safe. Accordingly, safety data, including AEs, vital signs, neurological surveys, ophthalmic tests, ECGs, and clinical laboratory tests, will be assessed by both the investigator and the sponsor prior to each dose escalation. Any available PK data may be reviewed but PK data are not required for the initial dose-escalation decisions. However, from Dose 4 onwards, LY3323795 PK data will be reviewed before escalation to the next subsequent dose level to verify that the projected median exposure does not exceed one tenth the NOAEL exposure established in rats (i.e. median area under the concentration-versus-time curve (AUC) will not exceed 3,450 ng $\cdot$ hour/mL and median Cmax will not exceed 214 ng/mL) (see Section 7.4.1). PK samples up to 96 hours postdose will be required to conduct the PK data reviews. The 96-hour PK sampling period may be adjusted based on emerging PK data. Plasma A $\beta$  data may also be reviewed to assess the PD profile. Time points for PK and PD sampling and required safety assessments may be modified based on emerging PK and safety results.

In addition to the reviews of PK data required after Dose 4 for the purposes of dose escalation, interim access to PK and PD (including plasma A $\beta$ ) data will occur after the anticipated 1-mg dose (Dose 2) and 10-mg dose (Dose 4) of Part A. Data from this interim access to data (IAD) reviews, as well as results of the PK IADs following Doses 4, 5, and 6, will be used at different points to select doses in Part B (see [Figure SCAA.1](#)).

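### The stopping rules in Protocol Section 7.4.1 can lose a mandatory stop because an impairing adverse event also poses a risk to the subject

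*Protocol*

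**What the plan says.** Section 7.4.1 of the Protocol gives five scenarios. If any one occurs, "dosing at the current level and further dose escalation will be discontinued". Three of them apply to specific kinds of event: one related SAE (criterion 1), ophthalmic findings in two or more subjects (criterion 4) and QTc readings in two or more subjects (criterion 5). The other two cover general adverse events:

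- Criterion 2 needs two or more subjects at the same dose level with moderate or severe AEs that impair normal activities "and are considered related to LY3323795, but do not meet the CSE criteria". The events need not resemble each other.
- Criterion 3 needs two or more "subjects at the same dose level experience similar CSEs considered related to LY3323795". The protocol does not define similar.

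The CSE definition is in Section 7.3: "A CSE will be defined as a moderate-to-severe AE, abnormal clinical sign, or clinical laboratory finding that may pose a risk" to the subject's well-being. A CSE can therefore be an impairing AE, but it can also be a sign or laboratory value that impairs nothing.

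Section 7.4.1 presumes causality: events "will be considered related to the investigational product unless there is clear evidence that the event is not related". The SAP does not restate or change the stopping criteria.

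**The concern.** Criteria 2 and 3 divide adverse events by whether they may put the subject at risk, and the riskier class faces the harder test. An impairing AE that poses no risk counts towards criterion 2 alongside any other such AE. If the same AE, with the same severity and impairment, is judged to pose a risk, it leaves criterion 2 and counts only if a second subject has a similar CSE. No criterion adds the two classes together.

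A stopping list in a first-in-human escalation should never become less likely to fire because an event is more dangerous. The main exposure is the decision to escalate in steps of roughly threefold. A missed stop could also carry further: the maximum tolerated dose from Part A caps the Part B doses (Section 5.1.2.1), and the Part C dose may be at most one-tenth of it (Section 5.5, Part C).

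Protection at the current dose level may gain less. After the two sentinels, "if the dose is well tolerated, dosing of the remaining 7 subjects in the cohort may begin", and the protocol does not say how those 7 are staggered. If they are dosed close together, few doses remain to be withheld once events appear.

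**Working it through.** **Reading the rule.** Take two subjects at one dose level. Each has one related moderate or severe AE that impairs normal activities and is not an SAE, an ophthalmic finding or a QTc reading.

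| Events | Alike? | Criterion 2 | Criterion 3 | Result |
|---|---|---|---|---|
| Two non-CSE AEs | either | met | – | stop |
| One CSE, one non-CSE AE | either | not met (one counts) | not met (one CSE) | no mandatory stop |
| Two CSEs | no | not met (none count) | not met | no mandatory stop |
| Two CSEs | yes | not met | met | stop |

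Reclassifying one event in the first row as a CSE gives the second row and removes the stop. A generous reading of similar shrinks the third row but leaves the second untouched.

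**How often this could happen.** The documents give no event rates and no operating characteristics for the list, so there is no planned figure to reproduce. The rates below are assumptions.

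Inputs:
- 6 LY3323795 subjects per dose level (Section 5.1.1).
- Assumed: independent subjects, at most one event each, all related, none an SAE, ophthalmic or QTc event.
- Assumed mixed case: CSE risk 0.05, all impairing, and impairing non-CSE AE risk 0.05, so 0.10 in total.

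Chance that two or more subjects have an event:
1 − 0.9^6 − 6 × 0.1 × 0.9^5 = 0.1143.

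Lower case, all CSEs alike. The only unstopped pattern is exactly one CSE and one non-CSE AE:
6 × 5 × 0.05 × 0.05 × 0.9^4 = 0.0492.

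Upper case, no two CSEs alike. A stop then needs two or more non-CSE AEs, which has probability 1 − 0.95^6 − 6 × 0.05 × 0.95^5 = 0.03277. The unstopped share is 0.11426 − 0.03277 = 0.08149, or 8.1%.

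Between these, the chance that n CSEs are all unlike is n! × e_n, where e_n is the elementary symmetric polynomial of the kind probabilities. Summing the multinomial over outcomes with two or more events, at most one non-CSE AE and all CSEs unlike gives the unstopped probability. After the fix, the condition becomes at most one impairing event of either class, with all CSEs unlike.

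| How CSEs split into kinds | Current rule | After fix, all CSEs impair | After fix, half impair |
|---|---|---|---|
| All alike | 0.0492 | 0 | 0.0246 |
| Two equal kinds | 0.0642 | 0 | 0.0345 |
| Five kinds, one with 70% | 0.0642 | 0 | 0.0344 |
| Five equal kinds | 0.0743 | 0 | 0.0409 |
| None alike | 0.0815 | 0 | 0.0454 |

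The last column is what remains when half the CSEs are non-impairing signs or laboratory findings, which the fix does not reach. The current-rule column is the same whether all or half of the CSEs impair, because criteria 2 and 3 do not ask whether a CSE impairs.

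With CSEs only, at an assumed 10% risk and all impairing, the unstopped probability under the current rule is 0 if all are alike, 0.0492 with two equal kinds, 0.0502 if one of five kinds takes 70%, 0.0860 with five equal kinds, and 0.1143 if none are alike.

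**The case against.** The strongest reply is that the list is not the only barrier. Under Section 5.1.1.1, safety data "will be assessed by both the investigator and the sponsor prior to each dose escalation", and the preceding dose must have been shown to be safe before the next is given. Section 7.4.1 adds that "No dose escalation can occur without prior discussion and agreement between the investigator and" the sponsor's team, and Section 10.3.5 leaves that team unblinded. Someone would have to judge a dose safe after two of six active subjects had related impairing events. The SAE definition in Section 9.2.1 also lets the investigator class an event as serious on medical judgment, and one related SAE stops dosing. Relatedness, impairment, risk and similarity are themselves judgments, so amending the list does not make it objective.

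This stands as mitigation. It lowers the chance of an unsafe escalation, and the SAE route may catch the worst CSEs. It does not repair the rule: none of these safeguards is automatic for a non-serious CSE, and a mandatory list exists so that stopping does not depend on discretion alone.

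The illustration also depends on at most one event per subject. A subject with a CSE and a separate related impairing non-CSE AE still counts under criterion 2. If half of CSE subjects had both, the 4.9% would become 0.0492 × 0.5 = 2.5%; at 80%, 0.0492 × 0.2 = 1.0%. So 4.9% is not a floor.

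Requiring similarity could be defended as a filter against coincidence, since presumed relatedness lets background events count. That defence fails here, because two unlike non-CSE AEs already stop dosing under the same presumption.

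**Conclusion.** The concern holds and should be fixed. As written, judging one of two related impairing AEs to be a risk to the subject can remove a mandatory stop, and nothing elsewhere in the Protocol or SAP corrects this. That conclusion rests on the wording alone.

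The size is illustrative. On the assumed mixed-case rates, 4.9% to 8.1% of dose levels would have two or more subjects with impairing events and no required stop, out of 11.4% with two or more such subjects. The 4.9% needs no assumption about what similar means, but it does need the assumed rates and one event per subject. The consequence is softened by the review and agreement required before each escalation, so this is a flaw in the mandatory rule and not an absence of safety oversight.

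**What to change.** In criterion 2 of Section 7.4.1, delete the closing exclusion of events that meet the CSE criteria. Two or more subjects at the same dose level with related moderate or severe AEs that impair normal activities would then stop dosing, whether or not the events are CSEs and whether or not they are alike. Keep criterion 3.

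State in the protocol what this leaves to the safety review: two unlike non-impairing CSEs, one non-impairing CSE with one impairing AE, and one non-impairing CSE with an unlike impairing CSE. Whether to drop or define similar in criterion 3 is for the clinical team.

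The change is one clause in an amendment, with no new data or procedures. The cost is more frequent stopping. In the mixed illustration the added stops are 4.9% to 8.1% of dose levels if all CSEs impair activities, and 2.5% (0.0492 − 0.0246) to 3.6% (0.0815 − 0.0454) if half do. With all CSEs impairing and the rates constant over all six Part A dose levels, the chance of at least one such stop rises to 1 − (1 − 0.1143)^6 = 52%. Under the current rule it is 33% if all CSEs are alike (per-level stop 0.1143 − 0.0492 = 0.0651) or 18% if none are (0.0328). Some added stops could be due to background events. Section 7.4.1 already allows dosing to continue at lower doses after a stop.
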